## 7. STUDY DESIGN

### 7.1 STUDY DESIGN DIAGRAM

**Non-invasive cardiac screening tests:** The choice of non-invasive test(s) will be according to the existing practice of each transplant centre. Although the accuracy of inotropic stress echocardiography to identify occlusive CAD is somewhat better than vasodilator stress nuclear perfusion imaging, both abnormal Myocardial Perfusion Scintigraphy and Dobutamine Stress Echo have prognostic value for cardiac events and mortality in patients with renal failure, and are used extensively in clinical practice.(11, 33) The type of test used will be documented in all instances.

**Investigation and management of an abnormal screening test:** The management of an abnormal screening test including performance of coronary angiography as well as treatment of coronary stenoses will be carried out as per the usual standard of care in individual transplant centres and will not be influenced by the investigators or study personnel in any way.

## 7.2 STUDY TYPE & DESIGN & SCHEDULE

This trial is a pragmatic multi-centre, randomized, parallel group definitive trial incorporating an economic evaluation and involving sites in Canada, Australia and New Zealand. Asymptomatic waitlisted patients will be randomised to no screening versus routine screening for CAD (i.e. Exercise Stress test, Myocardial Perfusion Scintigraphy or Dobutamine Stress Echo) as per the current standard of care at each centre.

**Intervention:** Patients randomized to no screening will **not** undergo regular non-invasive testing for CAD while on the wait list.

**Control:** Patients randomized to routine screening will undergo non-invasive testing for CAD every year or second yearly as determined by local centre practice.

**All:** Patients in either group who develop symptoms of angina or an angina equivalent at any stage will be investigated according to the local standard of care, which may include the use of non-invasive or invasive cardiac testing.

**Table 4: Study schedule**

Case Report Forms (CRF)	Baseline data	6m	12m	18m	24m	30m	36m	42m	48m	54m	60m	12m
CRF1 - Screening	✓											
CRF2 - Baseline data	✓											
CRF3 - Randomisation	✓											
CRF4a - Wait-list follow up	✓											
QoL Survey												
KDQoL-36 												
EQSD												
Events & outcomes												
CRF5 - Non-Transplant hospitalisation												
CRF6 - Transplant hospitalisation												
CRF4b - Post-transplant Follow up												
If patient is transplanted, move to arm 2 and follow new schedule of follow-up												
CRF7 - planned CAD screening test												
CRF9 - Missed CAD screening test												
CRF10 - Coronary angiogram												
CRF11 - Revascularisation												
CRF12 - Death												
CRF13 - Non-fatal MI												
CRF14 - Unstable angina												
CRF15 - Stroke												
CRF16 - Bleeding												
CRF17 - Wait list hold												
CRF18 - Wait list removal												
CRF19 - Wait list reactivation												
CRF20 - Withdrawal												

\* complete if event occurs

 Mandatory survey for Australia & NZ, optional for Canada

### 7.3 TESTING PROCEDURES

**Non-invasive cardiac screening tests:** The choice of non-invasive test(s) will be according to the existing practice of each transplant centre. Although the accuracy of inotropic stress

echocardiography to identify occlusive CAD is somewhat better than vasodilator stress nuclear perfusion imaging, both abnormal Myocardial Perfusion Scintigraphy and Dobutamine Stress Echo have prognostic value for cardiac events and mortality in patients with renal failure, and are used extensively in clinical practice.(11, 33) The type of test used will be documented in all instances.

**Investigation and management of an abnormal screening test:** The management of an abnormal screening test including performance of coronary angiography as well as treatment of coronary stenoses will be carried out as per the usual standard of care in individual transplant centres and will not be influenced by the investigators or study personnel in any way.

#### 7.4 STANDARD CARE AND ADDITIONAL TO STANDARD CARE PROCEDURES

**Management of patients who develop clinical symptoms of CAD:** Any patient, regardless of randomised trial allocation, developing clinical symptoms of CAD (e.g. angina, congestive heart failure, or new arrhythmias) will be evaluated according to the standard of care in individual transplant centres *and may include the use of non-invasive cardiac stress testing.* Management of symptomatic CAD including revascularization will be according to the standard of care at the local transplant centre.

Other than the use of cardiac screening tests, patient management will be as per the usual standard of care in participating transplant centres. In both study groups, the frequency and content of clinical re-evaluations will be according to the existing practice of the transplant centres participating in the study. Such evaluations may include cardiology consultations. Clinical evaluations by the transplant centre during wait-listing will be recorded in both groups. Interventions to prevent cardiovascular disease events may be used. Study personnel will document all surgical and medical interventions for CAD. The use of cardio-protective medications (aspirin, beta-blockers, medications that block activation of the renin angiotensin system, lipid lowering agents) will be documented every six months in all trial participants. However, the use of lipid lowering agents, aspirin, and beta-blockers remain controversial due to the lack of definitive evidence regarding efficacy in ESKD patient, and their use is likely to vary between centres and between physicians at the same centre.(9, 34) Similarly behavioural therapies such as participation in weight loss, smoking cessation or healthy heart programs may be used. Medical and behavioural treatments will not be specified in the trial but will be documented by study personnel.

#### 7.5 RANDOMISATION

Allocation of participants to trial groups will be done using the same web-based randomization system used in our pilot trial. Patients will be stratified by centre and diabetes. The randomization process will consist of a computer-generated random listing of the group allocations stratified as above in variable permuted block sizes that will not be known to the investigators. The system will have backup in the form of a statistician and designated research assistant at the coordinating centre and only these individuals will know the randomization codes. After confirming eligibility and obtaining consent, the study nurse will access the trial website and provide the subject's unique ID. The web site will provide the next available randomization number.

#### 7.6 ECONOMIC METHODOLOGY

*Outline of the within-trial analysis*

A cost-effectiveness and cost-utility analysis of no screening compared to usual screening will be conducted from an Australian and Canadian health system perspective.

#### *Outcomes for the analysis*

The analysis will report the cost per MACE avoided; the cost per life year gained; and the cost per quality adjusted life year (QALY) gained of no screening compared to usual screening.

#### *Analysis methods*

A cost-utility analysis will be undertaken for this non-inferiority trial.

#### *Censoring of costs and outcomes*

Censoring of cost data may occur if: the cost event eg. hospitalization continues beyond the 4 year follow-up time; the cost data collection for some participants does not start at randomization; or if participants are lost to follow-up. A comparison of the clinical characteristics of participants with complete versus censored cost data will be tabulated. The method for addressing censored cost data will be determined after investigation of the pattern of missing data (e.g. missing completely at random, missing at random, missing not at random) using the Lin method, the Bang & Tsiatis method or multiple imputation methods.(35) Censoring of outcome data may occur if patients are lost to follow up. Survival analysis methods such as Kaplan Meier Sample Average (KMSA) or Inverse Probability Weighting (IPW) will be undertaken.

#### *Statistical methods for analysis of economic data*

Skewed cost data: Cost data are likely to be right skewed as they are bounded by zero (i.e. can't be negative); have no upper bound, and a small number of patients will likely incur very high costs, affecting the mean. The cost distribution will be plotted in a histogram and non-parametric bootstrapping will be used for analysis. (36)

#### *Data validation*

Identification of resource use in the trial case report forms and patient diaries will be validated through a cross check with treating clinicians (nephrologists and cardiologists); by comparison with the published literature; and for Australian participants through cross checks with the Admitted Patient Data Collection and Medicare data.

#### *Missing data*

It is anticipated in this trial that there may be some missing quality of life or resource use data. Investigation of the pattern of missing data (e.g. missing completely at random, missing at random, missing not at random) will determine the appropriate method for handling the missing data. For quality of life, a weighted mean value for the group sample may be used to 'fill in' the missing items. Depending on the amount of missing data, multiple imputation will be considered.

#### *Costs*

Costs will include all CAD related health system resource use including screening and subsequent treatments, doctor's visits and in-patient hospitalisations.

#### *Individual participant resource use*

Data on resource use will be obtained in two ways. First through identification of tests, procedures and doctor's visits related to cardiac and renal management for all study participants from randomisation to study end as recorded in the patient diaries and trial case report forms. Second, Australian and Canadian participants will have their records linked to regional or provincial administrative data to capture units of resource use including in-patient, ambulatory care, medication use, and physician visits.

#### *Unit costs*

Valuation of resource use will be obtained using relevant costs (Australian-Refined Diagnosis Related Groups (AR-DRG); CIHI CMG+, etc.).)

#### *Results*

The mean and total volume of major categories of resource use (e.g. diagnostic tests; doctor's visits; revascularization procedures; and hospitalisations) will be reported for each group. The difference in the volume of resource use for each group and 95% confidence intervals for the difference will be reported.

#### *Total costs*

The total cost will be calculated by multiplying the arithmetic mean cost by the number of participants in each group. Mean costs with standard deviations and total costs for each group will be reported in Australian dollars for the most recent reference year, discounted at 5% per annum. The difference in total costs will be assessed using the student t test and/or analysis of variance (ANOVA). Total costs will also be adjusted for relevant baseline characteristics (e.g. age, sex).

Benefits will include:(i) quality of life, measured annually with the KDQOL-36™ and EQ-5D-5L surveys; (ii) the proportion of participants who avoid MACE; (iii) life years gained and (iv) QALY gained at year 2 (12 months post randomisation) and year 4 (study end).

#### *Participant utilities*

The EQ-5D-5L will be administered to all trial participants at baseline and every 6 months throughout the trial.

#### *Cost-effectiveness and cost-utility analyses*

Using the mean discounted costs in each trial arm, and the mean discounted benefits in each arm, the incremental cost per life year gained and cost per QALY gained of the no screening group compared with regular screening group will be calculated; results will be plotted on a cost-effectiveness plane. Bootstrapping will be used to estimate a distribution around costs and health outcomes, and to calculate confidence intervals around incremental cost-effectiveness ratios.(39)A cost-effectiveness acceptability curve (CEAC) will be plotted, providing information about the probability that the intervention is cost-effective given a decision maker's willingness to pay for a QALY gained.(39)

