#### *Sensitivity analysis*

One-way sensitivity analyses will be conducted around key variables, including the most expensive items of resource use, and the frequency of cardiac screening in the usual care arm: i.e. every year versus every 2 years. Sensitivity analysis will be undertaken using an alternative QALY weight obtained from the SF-6D a component of the KDQOL-36™ questionnaire using country-appropriate tariffs. In addition, sensitivity analyses will vary the discount rate from 0-6%.

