## **10. STATISTICAL METHODS**

### **10.1 SAMPLE SIZE ESTIMATION & JUSTIFICATION**

The target total sample size is 3306 patients from 23 sites (7 from Australia, 1 from NZ, 15 from Canada). This number of sites will provide a target number of 1000 patients from Australia, 100 from New Zealand and 2206 from Canada. This equates to recruitment of  $\leq 4$  patients per month per centre. This rate is feasible given current wait-list and transplant volumes from all countries.

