### **10.2 POWER CALCULATIONS**

We conservatively estimate an average MACE rate of 6%: MACE rates in the U.S. range from 8.7 % in the first year after a kidney transplant to 13.2 % per year on the waiting list.(41) Unpublished data in Australia and Canada show lower rates of 3% and 8% respectively. The lowest MACE rate would be observed if *all* patients underwent transplantation rapidly (i.e. one year wait-listing (MACE 8%), followed by one year of post transplant follow up (MACE 3%)). In this hypothetical scenario, the

[figure not shown]
average MACE rate would be 5.5%. We estimate that 50% of participants will receive a kidney transplant during the study - therefore the majority of patient follow up time will be accrued on the waiting list (when the MACE rate is high) rather than after a KTX justifying our estimated average MACE rate of 6%.

Using a MACE rate of 6% per year and non-inferiority defined as a Hazard Ratio (HR) of MACE  $< 1.25$ , randomization of **3306 patients** will give us 80% power using a two-sided 5% significance level to claim no screening is non-inferior to regular screening if the absolute difference in MACE in the no screening group is  $< 1.4\%$  higher (i.e. 7.4% versus 6.0 %) than in the regular screening group (Fig 2). This is lower than the 2% absolute increase in MACE Canadian transplant physicians indicated would be unacceptable in a survey prior to our pilot trial.

Enrolment of 3306 patients requires recruitment of  $\leq 4$  patients per month per centre. This rate is feasible, and was achieved in our pilot trial. Figure 2 shows the study power for MACE rates between 5 -13% per year. These calculations take into account the different study follow-up in Canada (5 years) and Australasia (4 years), and allow for a 10% drop-out rate.

Power calculations were performed using the **Non-inferiority Logrank Tests** in PASS 12 (NCSS, LLC. Kaysville, Utah, USA. [www.ncss.com](http://www.ncss.com)).

Figure 2: Study power for MACE rates

- For all power calculations, non-inferiority is defined as an absolute increase in the Hazard Ratio (HR) of MACE  $< 1.25$ , Two-sided alpha is 5%, and the total sample size is fixed at N=3306

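### Incremental QALYs come from arm means with no adjustment for baseline utility, although EQ-5D-5L is collected at baseline in everyone: the estimate is unbiased but keeps chance imbalance and loses precision

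*Protocol*

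**What the plan says.** All references are to the protocol. Section 7.6, under Cost-effectiveness and cost-utility analyses, obtains the cost per life year and per QALY "Using the mean discounted costs in each trial arm, and the mean discounted benefits in each arm". Uncertainty is handled by resampling: "Bootstrapping will be used to estimate a distribution around costs and health outcomes". The cost-effectiveness plane and the acceptability curve are built on the same increments.

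Under Participant utilities: "The EQ-5D-5L will be administered to all trial participants at baseline and every 6 months throughout the trial". Baseline utility is therefore scheduled for everyone.

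Under Total costs, adjustment is planned, but for costs: "Total costs will also be adjusted for relevant baseline characteristics (e.g. age, sex". No matching sentence exists for QALYs. The same subsection lists the benefits, including "QALY gained at year 2 (12 months post randomisation) and year 4 (study end". Its label equating year 2 with 12 months needs correcting, but the point here does not depend on it.

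Under Sensitivity analysis, the protocol varies key resource items, screening frequency and the discount rate, and adds another utility source: "Sensitivity analysis will be undertaken using an alternative QALY weight obtained from the SF-6D". None of these adjusts for baseline utility.

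Three other places bear on the point:
- Section 7.5 stratifies randomisation by centre and diabetes.
- Section 7.6, under Censoring of costs and outcomes, plans a Kaplan-Meier sample average or inverse probability weighting for censored outcomes.
- Section 10.3 adjusts every analysis for site, and adds a further adjusted analysis if a baseline characteristic turns out to be unbalanced.

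**The concern.** Baseline utility is the starting height of each participant's QALY area and usually predicts later utility. Randomisation does not stratify on it, so the arms will differ in it by chance. With a plain difference in means, the part of that difference that persists is counted as QALYs gained or lost through no screening.

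The lay summary in section 5.1 says the investigators expect no difference between the strategies. If the QALY difference is also small, a shift of a few hundredths of a QALY matters to a ratio with a small denominator and to the quadrant of the plane in which the result falls. The bootstrap reports this extra variation but does not remove it.

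**Working it through.** The protocol states no QALY precision, utility SD or correlation, so there is no figure of its own to reproduce. The size is shown over assumed ranges.

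**Inputs from the protocol**
- Sample size: "The target total sample size is 3306 patients from 23 sites". The allocation ratio is not stated. Assuming 1:1, there are 3306 / 2 = 1653 per arm.
- Discounting: 5% per annum, stated for costs and applied here to QALYs as an assumption.
- Horizon: 4 years, the later QALY time point.
- Dropout: the power calculations "allow for a 10% drop-out rate".

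**Assumed inputs**
- Utility SD: 0.15-0.30.
- Carry-over b (slope of follow-up utility on baseline utility): 0.4-0.8.
- Correlation r between baseline utility and QALYs: 0.3-0.6.

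**Step 1: chance baseline difference.** SE = SD × √(2 / n per arm), and √(2 / 1653) = 0.0348.
- SD 0.15: SE = 0.0052.
- SD 0.25: SE = 0.0087.
- SD 0.30: SE = 0.0104.

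**Step 2: discounted years.** (1 − 1.05⁻⁴) / ln 1.05 = 3.63, before deaths and censoring.

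**Step 3: amount carried into incremental QALYs.** Shift = SE × 3.63 × b.
- Lowest: 0.0052 × 3.63 × 0.4 = 0.008.
- Middle (SD 0.25, b 0.6): 0.0087 × 3.63 × 0.6 = 0.019.
- Highest: 0.0104 × 3.63 × 0.8 = 0.030.

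Multiplying by 1.96 gives 95% limits of about ±0.015 to ±0.060, and ±0.037 in the middle case. With 10% dropout (1487 per arm) the one-SE range is 0.008-0.032, so dropout changes little.

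**Step 4: precision.** Adjusting for baseline utility multiplies the variance of the QALY difference by 1 − r².

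| r | variance factor | SE reduction | equivalent unadjusted N |
|---|---|---|---|
| 0.3 | 0.91 | 5% | 3306 / 0.91 = 3633 |
| 0.5 | 0.75 | 13% | 3306 / 0.75 = 4408 |
| 0.6 | 0.64 | 20% | 3306 / 0.64 = 5166 |

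**Step 5: simulation check.** 2000 trials were simulated with 1653 per arm, no true effect, 4 years of follow-up, a death hazard of 0.06 per year, SD 0.25 and a correlation of about 0.5.
- The mean unadjusted difference was 0.0008 against a true value of 0, so there is no bias.
- The SD of the QALY difference fell from 0.0335 unadjusted to 0.0290 adjusted, a variance ratio of 0.75.
- The correlation of the estimate with the baseline imbalance fell from 0.50 to about 0.

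**The case against.** The strongest reply is that this is analysis-plan detail. The protocol does not call the means raw. The same sentence uses the same word for costs, which are adjusted elsewhere, so the word mean does not exclude adjustment. A separate analysis plan, not available here, may supply the covariates. This stands in part. Even so, the protocol does choose an estimator and does mention baseline adjustment, and it attaches that adjustment to costs alone.

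A reader might also infer several stronger things that the protocol does not support.
- *That the QALY result is biased.* It is not. Chance imbalance is part of the sampling variation that the bootstrap already expresses, and the loss is one of efficiency.
- *That simple averages of observed QALYs will be used regardless of follow-up.* The censoring methods in section 7.6 say otherwise.
- *That centre is left out.* Section 10.3 adjusts all analyses for site, which on its face covers the QALY comparison. Its imbalance rule, however, is conditional, yields only an additional analysis, and names neither utility nor QALYs.
- *That adjustment settles the sign of the QALY difference.* If the true difference is near zero, chance sets the sign under any estimator. In the simulation, adjustment lowered the SD by only about 13%.
- *That one SE of imbalance is worth 0.035 QALY.* That figure is 0.0087 × 4, with no discounting, no deaths and full persistence. A QALY-on-baseline slope of 4 with SD 0.25 and r of 0.5-0.6 requires a QALY SD of 4 × 0.25 / r = 2.0-1.67. The largest SD possible on a 0-4 scale is 2.0, so the figure sits badly with those correlations.

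**Conclusion.** The point holds as one of chance imbalance and lost precision in a secondary, economic endpoint. The protocol takes incremental QALYs from arm means and plans baseline adjustment for costs only, while collecting the most relevant covariate in everyone.

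Under the stated assumptions, one SE of imbalance is worth about 0.008-0.030 QALY over 4 years, somewhat less once deaths and censoring are counted. The precision gain runs from slight at a correlation of 0.3 to substantial at 0.6. All of these sizes depend on the assumed SD, carry-over and correlation, and on 1:1 allocation. The clinical primary analysis is not affected. The change is worth making because it needs no new data for the EQ-5D-5L base case.

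**What to change.** Amend the Cost-effectiveness and cost-utility analyses text in section 7.6 as follows.
- **Base case:** take incremental QALYs from a regression on arm, baseline EQ-5D-5L utility, centre and diabetes. Centre is already implied by the site adjustment in section 10.3. Diabetes is the other randomisation factor.
- **Costs:** adjust them consistently, and state that the adjusted cost increment is the one used in the ratio.
- **Uncertainty:** fit both regressions inside each bootstrap replicate, and use the adjusted increments for the ICER, the plane and the acceptability curve.
- **Censoring and missing data:** combine the regression with the methods already planned in section 7.6, for example inverse-probability-weighted regression or multiple imputation. A regression on individual QALYs cannot otherwise use participants whose QALYs are censored.
- **SF-6D sensitivity analysis:** adjust for baseline SF-6D where KDQOL-36 was collected. The study schedule makes that survey optional in Canada, so the covariate may be missing for many of the 2206 planned Canadian participants.
- **Unadjusted result:** keep it as a sensitivity analysis.

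The cost is a wording change and slightly more analysis work. No visit or questionnaire is added.

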#### **4.2 STUDY DESIGN**

CARSK is a multicentre, non-inferiority, 2-parallel-arm randomised trial.

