## 5. INTRODUCTION/BACKGROUND INFORMATION

### 5.1 LAY SUMMARY

The CARSK trial will enrol people who are already on the kidney transplant waiting list, and who don't have any symptoms of new heart problems. The patients enrolled will stay in the study for a maximum of 4 years in Australia and New Zealand and 5 years in Canada. While they are in the study, people will be followed up as usual – they will not have to have any extra appointments but will receive a 6-monthly phone call to check wait-list status and exclude any CAD events. They will also be asked to complete cost and quality of life questionnaires. The trial will use chance to allocate people to either getting no regular heart testing while they wait for a kidney transplant, or to get regular (every year or every second year) heart testing. We will make sure everyone gets tested if they develop any symptoms of heart problems. The trial will measure what happens to people, and particularly whether they develop any heart problems, whether they get a kidney transplant, and whether they have any heart problems after a transplant. The study is important as we know the most common cause of death for people on dialysis or after a transplant is heart related. We don't know if finding heart disease and trying to treat it early, before it is bothering people, is a good idea – even though this is what is done at the moment. We think testing and treating people who don't have symptoms might cause more problems than it solves - it might remove them from the waiting list unnecessarily, or put them through tests and procedures or operations that they don't really need, and waste a lot of peoples' time and money without good reason. This CARSK study will help us work out whether regular testing is helpful, by showing us whether there is any difference to what happens to people if they are tested or not. The study investigators think it is likely that there will be no difference, so we have used best scientific principles to design the CARSK study to test whether we are right.

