**Does routine screening have other downsides?** Screening may paradoxically increase morbidity and mortality by: i) exposing patients to risk of angiography and revascularization procedures; or ii) by delaying or excluding patients from lifesaving kidney transplantation because of their perceived CAD status. In other settings, for example in most surgical candidates, screening is not beneficial. However, the goals of screening transplant candidates differ somewhat from other settings, and include not only prevention of peri-operative cardiac events, but also maintenance of transplant eligibility during wait-listing, and long-term post-transplant survival. The current standard of care may be harmful. The potential harmful outcomes related to the current strategy of screening and revascularization of asymptomatic transplant candidates are summarized in Table 1 below.

A recent joint Scientific Statement from the American Heart Association and the American College of Cardiology Foundation concluded “that there is no strong evidence for or against routine cardiac screening of asymptomatic transplant candidates” and that more evidence from randomized clinical trials was needed. The lack of evidence in the transplant setting has led to confusion about the optimal management of transplant candidates: the two major issues of uncertainty are whether to screen asymptomatic patients for occult CAD, and whether to revascularise coronary stenoses in asymptomatic, screen-detected patients.

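### The bootstrap confidence intervals planned around the cost-per-life-year and cost-per-QALY ratios cannot be interpreted if the effect difference is near zero, and mislead if no screening is cheaper and better; net benefit should be added

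*Protocol*

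**What the plan says.** The economic evaluation in Protocol section 7.6 is built on ratios. Under outcomes for the analysis: "The analysis will report the cost per MACE avoided; the cost per life year gained", followed by cost per QALY. The subsection on cost-effectiveness and cost-utility analyses defines "the incremental cost per life year gained and cost per QALY gained of the no screening group compared with regular screening group". It then uses bootstrapping for a distribution around costs and outcomes and "to calculate confidence intervals around incremental cost-effectiveness ratios". The same subsection plans a cost-effectiveness plane and an acceptability curve for willingness to pay per QALY.

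The setting is stated just as clearly. Section 4.2: "CARSK is a multicentre, non-inferiority, 2-parallel-arm randomised trial". Section 7.6, analysis methods: "A cost-utility analysis will be undertaken for this non-inferiority trial". Section 5.1: "The study investigators think it is likely that there will be no difference".

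Section 7.6 has no rule for an effect difference near zero or for replicates that fall in more than one quadrant of the plane, and it does not mention net benefit.

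**The concern.** A ratio has a readable confidence interval only when its denominator is clearly away from zero. Here the denominator is the difference in life years or QALYs, and one result the investigators expect is little or no difference. Section 5.2 presents screening as costly, so the natural expectation is a saving with a small effect difference of either sign.

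Three things then go wrong:

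- Replicates with a saving and a health gain give negative ratios, while replicates with a saving and a health loss give positive ones. Ordering them by size mixes opposite findings.
- Replicates with an effect close to zero give ratios of enormous size.
- Even if nearly all replicates show a saving and a gain, the size of the negative ratio does not rank them.

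Comparing benefits and costs is one of the two aims in section 4.3, so an error bar that cannot be read matters, although it lies outside the primary analysis.

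**Working it through.** The protocol gives no expected cost or QALY difference and no standard deviations, so there is no stated figure to reproduce. Every input below is an assumption.

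**Inputs.** Cost difference ΔC = -2,000 (SE 600). QALY difference ΔE = 0, 0.02, 0.05 or 0.10 (SE 0.03). Willingness to pay λ = 50,000 per QALY. ΔC and ΔE are drawn as independent normals. With the protocol's 3306 patients split 1:1 (1653 per arm; the ratio is not stated), an SE of 0.03 corresponds to a QALY SD of 0.03 / √(2/1653) ≈ 0.86.

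**Formulas.**

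- Ratio: ΔC/ΔE, with the 2.5th and 97.5th percentiles of the draws.
- Share of replicates with a QALY loss: Φ(-ΔE/0.03).
- Fieller criterion: g = (1.96 × 0.03/ΔE)² = (0.0588/ΔE)². The interval is unbounded if g ≥ 1, that is, when the 95% interval of ΔE includes zero.
- Net benefit: λΔE - ΔC, with SE = √((50,000 × 0.03)² + 600²) = √2,610,000 ≈ 1,616, so the half-width is 1.96 × 1,616 ≈ 3,167.

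| ΔE | QALY loss | g | Percentile interval of the ratio | Net benefit (95% interval) |
|---|---|---|---|---|
| 0 | 50% | infinite | -1.07 to +1.07 million | 2,000 (-1,200 to 5,200) |
| 0.02 | 25% | 8.6 | -865,000 to +835,000 | 3,000 (-200 to 6,200) |
| 0.05 | 5% | 1.4 | -319,000 to +188,000 | 4,500 (1,300 to 7,700) |
| 0.10 | 0.04% | 0.35 | -53,000 to -7,400 | 7,000 (3,800 to 10,200) |

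The ratio limits move by a few per cent between simulation runs, because the tails are so heavy. The net-benefit limits do not.

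**Range over the assumed SD.** For a QALY SD of 0.5 to 1.2, the SE is 0.017 to 0.042.

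| ΔE | QALY loss | g | Fieller interval |
|---|---|---|---|
| 0 | 50% | infinite | unbounded throughout |
| 0.02 | 12% to 32% | 2.9 to 16.7 | unbounded throughout |
| 0.05 | 0.2% to 11.6% | 0.46 to 2.68 | bounded only at the smallest SD |
| 0.10 | 0% to 0.8% | 0.12 to 0.67 | bounded throughout |

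**Why bounded is not enough.** In the last row of the first table the whole interval is negative. Take two replicates with the same saving of 2,000:

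- A gain of 0.05 QALY gives -2,000/0.05 = -40,000 and a net benefit of 2,500 + 2,000 = 4,500.
- A gain of 0.20 QALY gives -2,000/0.20 = -10,000 and a net benefit of 10,000 + 2,000 = 12,000.

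Here the better result lies nearer zero. Now hold the gain at 0.10 and raise the saving from 1,000 to 2,000. The ratio moves from -10,000 to -20,000, so the better result lies further from zero. The two limits of a negative interval therefore do not bracket worse and better outcomes.

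**The case against.** Four points can be made for the plan.

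**No zero effect is assumed.** A reader might infer from the lay summary that the denominator must straddle zero and the intervals are bound to be meaningless. The documents do not support that. The expectation of no difference concerns outcomes in general, and the non-inferiority margin concerns the MACE hazard ratio. No life-year or QALY difference is assumed. Section 5.1 says testing "might cause more problems than it solves", and section 5.2 says "Screening may paradoxically increase morbidity and mortality by" procedural risk and delayed or lost transplantation. A QALY gain without screening is thus also contemplated, and a gain of about 0.10 would give a bounded interval. This stands, and the point is conditional. But in that scenario, if no screening is also cheaper, the right report is dominance, and the interval still does not help.

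**The interval method is open.** Percentiles of ordered ratios are not named, and a separate analysis plan may specify the construction. This also stands. The percentile figures are an illustration. The Fieller column shows, however, that a different construction does not make the interval bounded near zero.

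**Not every ratio is given an interval.** A reader might take the planned intervals to cover cost per MACE avoided. The sentence on intervals follows only the life-year and QALY ratios, so the protocol does not expressly say so.

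**The decision is already supported.** The plane and the acceptability curve stay valid when effects cross zero. In the illustration with ΔE = 0, the curve would read Φ(2,000/1,616) ≈ 0.89 at 50,000. It would therefore be wrong to say that the economic analysis as a whole cannot inform a decision. The curve is specified for QALYs only, though, and it gives a probability without the size of the net gain or loss.

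**Conclusion.** The point holds in a limited form. The protocol commits to confidence intervals around two ratios in a design where one expected result makes those intervals unbounded or unreadable and another, a saving with a health gain, makes their limits misleading. Under the assumed SE of 0.03 the failure covers any observed QALY difference smaller than 0.0588. Over the assumed SD range that threshold runs from 1.96 × 0.0174 ≈ 0.034 to 1.96 × 0.0417 ≈ 0.082 QALY. Whether the trial lands there is unknown, because the documents give no cost or QALY difference.

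This is a weakness of reporting in the economic evaluation. It does not touch the primary MACE test, the sample size or the data collected.

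**What to change.** In section 7.6:

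1. Report incremental net monetary benefit with a bootstrap 95% interval at willingness-to-pay values stated in advance.
2. Beside it, report incremental cost and each incremental effect (MACE, life years, QALYs), each with its own 95% interval.
3. Keep the cost-effectiveness plane and the acceptability curve.
4. Give an interval for a cost-effectiveness ratio only when the 95% interval of the effect difference excludes zero and the replicates lie in quadrants where the ratio expresses a trade-off. Otherwise report dominance, or rely on the plane and net benefit.

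The cost is a change of wording and a little more analysis from replicates that will be generated anyway. The willingness-to-pay values have to be chosen beforehand, and readers who expect a ratio interval may not get one.
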